**A Split-Face Multi-Arm Randomized Clinical Trial
Showing the Efficacy & Safety of a Topical Mask After
Aesthetic Treatments**

[name]

A Split-Face Multi-Arm Randomized Clinical Trial Showing the Efficacy & Safety of a Topical Mask After Aesthetic Treatments.

Principal Investigator: [name]

[name]

[name]

[contact]

[contact]

Email Address: [contact]

Study Coordinator:

[name]

[name]

[name]

[contact]

[contact]

Email Addresses: [contact]

Sponsor: Velez

STATEMENT OF COMPLIANCE

The trial will be conducted in accordance with the ICH E6 and the Code of Federal Regulations on the Protection of Human Subjects (45 CFR Part 46). The Principal Investigator will assure that no deviation from, or changes to the protocol will take place without prior agreement from the sponsor and documented approval from the Institutional Review Board (IRB), except where necessary to eliminate an immediate hazard(s) to the trial participants. All personnel involved in the conduct of this study have completed Human Subjects Protection Training.

I agree to ensure that all staff members involved in the conduct of this study are informed about their obligations in meeting the above commitments.

[name]

PROTOCOL SUMMARY

Title: A Split-Face Multi-Arm Randomized Clinical Trial Showing the Efficacy & Safety of a Topical Mask After Aesthetic Treatments.

Précis: Subjects undergoing aesthetic facial treatments with either a fractionated non-ablative 1927nm Thulium laser (Sciton Moxi), ablative Erbium:Yag 2940nm (Sciton Contour), or Microneedling with Radiofrequency (Cutera Secret) will apply a face mask immediately after the procedure randomly on either their left or right side of their face with normal post-care on the other side of the face. Thirty minutes after the mask is applied to one side both regular photography and thermal photography will be done. In addition, subjects will fill out questionnaires and will be assessed by blinded evaluators for efficacy and potential side effects. Patients will wear the masks at home for at least two hours a day and return daily for photographs until deemed healed by the primary investigator (3-7 days). Patients will also fill out daily questionnaires.

Mask, Pain, Temperature, Post-Laser Care

Keywords:

Objectives: Primary Objective: To assess the efficacy of a facial mask in decreasing facial skin temperature after three different aesthetic treatments

Important Secondary Objectives:

1. To determine the safety and incidence of adverse events when using a Velez face mask after 3 different aesthetic treatments
2. To assess the change in the level of pain when using a Velez face mask after aesthetic treatments
3. To assess patient satisfaction with use of a Velez face mask after aesthetic treatments
4. To assess erythema when using a Velez face mask after aesthetic treatments
5. To assess healing time when using a Velez face mask

Primary

Endpoints:

Primary Endpoint:

The difference between the temperature on the mid-cheek (point inferior to the lateral limbus).

Important Secondary Endpoints:

1. The difference in the number of adverse events between the two sides of the face
2. The difference in pain scores on each side of their face as rated by subjects
3. The difference in patient satisfaction scores when rating the procedure on the left and right side of their face
4. The difference in erythema on the left and right side of subject's faces as graded by blinded evaluators doing live assessments 30 minutes after the procedure
5. The difference in healing time on the left and right side of subject's faces as graded by blinded evaluators looking at daily photographs

Population: Healthy adults aged 21 and over living in Palm Beach County, Florida.

Sample Size: 15

Study Sites: [name] &
[name]

Duration: 7 days

Study Agent: Velez Intense Hydration Mask

SCHEMATIC OF STUDY DESIGN

- Total n=15
- Screen potential subjects by inclusion and exclusion criteria

Day 0 Randomization

- Obtain informed consent, randomize into one of the following two groups
- Treatment Group 1 Right Side Velez Intense Hydration Mask
- Treatment Group 2 Left Side Velez Intense Hydration Mask

Day 0 Baseline assessments/ Study Intervention

- Baseline Assessments:
 - Pre-procedure pictures taken with Canfield's imaging system (Front, Right and Left Views)
- Study Intervention:
 - 1st Arm (n=5)
Non-ablative fractionated Thulium laser (Sciton Moxi) will be performed on level 3 and an Intense Hydration Mask will be applied to one side of the face with nothing on the other side for 30 minutes. After photos and evaluation, a hydration serum will be applied to both sides and patients will be sent home with masks to be worn at least 2 hours every day until deemed fully healed by the investigator
 - 2nd Arm (n=5)
Ablative full Erbium:Yag laser (Sciton Contour) will be performed at 200 microns and an Intense Hydration Mask will be applied to one side of the face with nothing on the other side for 30 minutes. After photos and evaluation, Vaseline will be applied on both sides of the face and the patient will be sent home with masks to be worn at least 2 hours every day until deemed fully healed by the investigator
 - 3rd Arm (n=5)
Microneedling with RF (Cutera Secret) will be done with a non-insulated needle at a depth of 200 and an Intense Hydration Mask will be applied to one side of the face with nothing on the other side for 30 minutes. After photos and evaluation, a hydrating serum will be applied on both sides of the face and the patient will be sent home with masks to be worn at least 2 hours every day until deemed fully healed by the investigator

All Arms

- Post-procedure pictures and questionnaires to be completed by subjects 30 minutes after the procedure
- Safety analysis and erythema scale to be performed by blind evaluators and a compliance analysis performed by study coordinator

Day 1-7 Follow-up assessments

- Daily in office follow-up assessments of study endpoints and safety until primary investigator deems patients healed from the procedure

1st Arm (n=5) Non-ablative fractionated Thulium laser (Sciton Moxi)

Post-procedure pictures and questionnaires to be completed by subjects for 3-7 days as determined daily by the primary investigator

2nd Arm (n=5) Ablative full Erbium:Yag laser (Sciton Contour)

Post-procedure pictures and questionnaires to be completed by subjects daily for 3-7 days as determined daily by the primary investigator

3rd Arm (n=5) Microneedling with RF (Cutera Secret)

Post-procedure pictures and questionnaires to be completed by subjects daily for 3-7 days as determined daily by the primary investigator

2 INTRODUCTION: BACKGROUND INFORMATION AND SCIENTIFIC RATIONALE

2.1 BACKGROUND INFORMATION

Aesthetic procedures are gaining popularity; however patients are always interested in less downtime and pain. With non-ablative laser and microneedling with radiofrequency, patients experience less, however even the few hours of pain and erythema may be decreased by post-procedure products making these treatments even easier to tolerate with less downtime. Additionally, ablative laser resurfacing still provides the best cosmetic results, however the pain and downtime often limits who is willing to do the procedure. Products that can decrease pain and erythema as well as quicken the healing phase are needed to enable more patients to undergo these cosmetic treatments.

While topical ice or a fan are sometimes used to decrease the pain and heat associated with procedures, these require the patient to remain in the office often in an exam room to either hold the ice or to utilize a specialized fan (Zimmer Chiller). This elongates the procedure time for both the patient and the treating provider. The advantage of the face mask is that it is self-adhering to the face and requires no additional time in the office or specialized planning since the masks do not need to be kept in a fridge. Velez intense hydration masks are made of bio cellulose material obtained from vegetable raw materials and are self-adhering providing mobility and immediate comfort.

2.2 RATIONALE

There are many different types of post-procedure masks that are reported to reduce pain and erythema, however none that have quantitative scientific data or publications to support their claims. This clinical trial will quantitatively show whether the Velez hydration masks are able to reduce post-procedure skin temperature, patient pain levels, erythema and healing time.

2.3 POTENTIAL RISKS AND BENEFITS

2.3.1 KNOWN POTENTIAL RISKS & RISK ANALYSIS

Potential risk of the mask includes swelling, itching, pain, dermatitis, erythema, or hypersensitivity.

Potential risk of the cosmetic treatments include swelling, itching, pain, dermatitis, erythema, infection, bleeding or scarring.

To mitigate the risk, patients will be educated on how to properly care for their skin post-procedure and all patients in the ablative arm will be receiving oral antibiotics and antivirals for infection prevention.

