3 STUDY DESIGN, OBJECTIVES, AND ENDPOINTS

3.1 DESCRIPTION OF THE STUDY DESIGN

- A Prospective, Multi-Arm, Split-Face, Randomized Clinical Trial
- 2 Study Centers
- Study agent: Velez Intense Hydration Mask
- Study Intervention on Day 0
- Live evaluations by Blinded Evaluators on Day 0
- Daily photographic evaluations by Blinded Evaluators

This will be a prospective, multi-arm, evaluator blind, split-face, clinical trial in which subjects will be randomized to 2 groups in 3 separate arms.

1st Arm (n=5) Non-ablative fractionated Thulium laser (Sciton Moxi)

2nd Arm (n=5) Ablative full Erbium:Yag laser (Sciton Contour)

3rd Arm (n=5) Microneedling with RF (Cutera Secret)

In each arm, there will be two groups

1st group: Velez Intense Hydration Facemask on the left side of their face and nothing on the right

2nd group: Velez Intense Hydration Facemask on the right side of their face and nothing on the left side

Both groups will be utilizing the same safety and comfort protocols established by the practice which include the use of topical numbing cream (B.L.T.) before the laser procedure and cleansing with a makeup wipe and alcohol.

After the procedure a blind evaluator will be grading the subjects' erythema, edema, and any side effects. A compliance analysis performed by study coordinator will be done each visit.

Thirty minutes after the laser procedure, digital photography using Canfield's imaging system, and a thermal camera will be done. In addition, a subject questionnaire on satisfaction, erythema, edema and pain levels after the procedure will be completed. Patients will then have the typical post-care treatment on both sides of their face such as Vaseline for laser resurfacing and a hydrating serum for the Moxi and Microneedling. They will apply the mask at home for at least two hours each day and then return to the office daily for questionnaires and photographs until deemed fully healed by the primary investigator.

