6.2.2 ENROLLMENT/BASELINE

Enrollment/Baseline Visit (Visit 1, Day 0)

- Review in depth the study design with subjects and obtain informed consent of potential participants verified by signature
- Perform examination and verbally review subject's medications and medical history to determine eligibility based on inclusion/exclusion criteria.
- Verify all inclusion/exclusion criteria.
- Obtain demographic information
- Randomization
- Perform either a Sciton Moxi, Sciton Erbium, or Secret RF treatments to subject's face, and then apply a half mask on one side of the face according to randomized groups.
- Record adverse events as reported by participant or observed by investigator or blind evaluator.
- Perform protocol adherence check by study coordinator
- Collect post-procedure subject questionnaires
- Take post-procedure photos

- After photographs and blind evaluation both side of the face will be treated with the normal post-procedure care such as Vaseline for laser resurfacing and a Hydrating serum for Moxi and Microneedling. Additional masks will be given to patients to wear for 2 hours at home each day until deemed healed by the primary investigator.

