6.4 PROPHYLACTIC MEDICATIONS, TREATMENTS, AND PROCEDURES

If the patient has a history of herpes simplex on the face, they will be allowed to use prophylactic anti-viral medications.

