6.5 RESCUE MEDICATIONS, TREATMENTS, AND PROCEDURES

If patients develop an infection during the trial, they will be prescribed the appropriate anti-viral or anti-bacterial medication but will continue in the study.

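### Section 2.3.1 commits every ablative-arm patient to antibiotics and antivirals, but the prophylaxis section states a narrower policy and no procedural section delivers the commitment

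*Combined protocol and SAP*

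**What the plan says.** Section 2.3.1 (Known Potential Risks & Risk Analysis) lists infection among the risks of the cosmetic treatments. It then gives two mitigations: teaching patients how to care for their skin, and a drug measure for one arm, "all patients in the ablative arm will be receiving oral antibiotics and antivirals for infection prevention".

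Section 6.4 (Prophylactic Medications, Treatments, and Procedures; the number 6.4 is also used for Subject Questionnaires) consists of one sentence: "If the patient has a history of herpes simplex on the face, they will be allowed to use prophylactic anti-viral medications".

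The only other provision for anti-infective drugs is in section 6.5 on rescue, and it applies once an infection has occurred: "If patients develop an infection during the trial, they will be prescribed the appropriate anti-viral or anti-bacterial medication but will continue in the study".

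The procedural text for the ablative arm in the Schematic of Study Design gives the laser, the half mask for 30 minutes, and then: "After photos and evaluation, Vaseline will be applied on both sides of the face and the patient will be sent home with masks". The Day 0 list in 6.2.2 says that "both side of the face will be treated with the normal post-procedure care such as Vaseline for laser resurfacing". Neither mentions an antibiotic or an antiviral.

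**The concern.** A risk section tells the IRB and the patient how a hazard will be controlled. The procedural sections tell staff what to do. Here the control promised in the first kind of section is not found in the second, and the section that carries the subject in its title describes a smaller measure.

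The stake is patient safety in the arm that the protocol itself singles out for prophylaxis. In the text available, the statement in 2.3.1 is the only drug-based measure that the protocol requires for preventing infection. There is also a record-keeping consequence. Section 10.3 treats any noncompliance with the protocol as a deviation. An ablative-arm patient who received no prophylaxis would plainly be a deviation under 2.3.1, but not evidently one under 6.4.

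**Working it through.** The plan gives no figure to reproduce and no formula applies. The check is a comparison of the sections, followed by a count of the patients affected.

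**Step 1: the two policy statements side by side.**

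- Who is covered: 2.3.1, every ablative-arm patient; 6.4, any patient with a facial herpes simplex history, with no arm named.
- What is given: 2.3.1, oral antibiotics and antivirals; 6.4, antivirals alone.
- Force: 2.3.1, an unconditional statement that patients receive the drugs; 6.4, a permission.

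They differ on all three.

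**Step 2: whether another section delivers the 2.3.1 commitment.**

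- Schematic, ablative arm: laser, half mask, photographs and evaluation, Vaseline, take-home masks. No anti-infective step.
- 6.2.1 Screening: patients are given instructions for preparing for the first visit. The content is not stated.
- 6.2.2 Day 0: consent, examination, randomization, treatment, mask, adverse events, questionnaires, photographs, usual post-care. No prescribing or dispensing step.
- 6.3.3 Follow-up: adverse events, photographs, decision on return. No check that prophylaxis was taken.
- 6.3.7 Schedule of events: no row for prophylaxis.
- 3.1: refers to the practice's own safety and comfort protocols, but the items it names are numbing cream and cleansing.
- 6.5: treatment after an infection, not prevention.

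No section in this list carries out the commitment.

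**Step 3: how many patients depend on 2.3.1 alone.** Section 3.1 puts 5 patients in the ablative arm out of 3 × 5 = 15. Let k be the number of those 5 with a facial herpes history. The documents do not give k. Section 4.2 excludes a current outbreak, not a history, so k can be anything from 0 to 5.

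- Antibiotics: 6.4 covers none, so all 5 depend on 2.3.1, whatever k is.
- Antivirals: 6.4 covers k patients, so 5 − k depend on 2.3.1, between 0 and 5.
- Prophylaxis as a requirement rather than a permission: all 5 depend on 2.3.1, whatever k is.

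The antibiotic gap is therefore the firmest part of the point. It affects the whole arm and does not depend on any unknown.

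**The case against.** The strongest reply is that both sections can be followed at once. Section 6.4 does not contain the word only and prohibits nothing. It can be read as a general allowance for patients in the other two arms who have a herpes history, while 2.3.1 sets a specific rule for the ablative arm. The section on prohibited medications bars anticoagulants, corticosteroids and immune-modulating drugs, not anti-infectives. Section 2.3.1 is part of the same protocol and binds the same investigators. This stands: a reader might infer a flat contradiction, or that 6.4 restricts prophylaxis to herpes patients, and the text supports neither. It does not close the gap. The reader has to supply that reading, because 6.4 names no arm, and even on that reading no procedural section provides for the antibiotics.

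The missing schedule row is weak evidence taken alone. The table also has no row for numbing cream, Vaseline, hydrating serum or the pregnancy test. Its absence counts only together with the silence of the arm description and the Day 0 list.

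Other safeguards exist: in-office visits each day until healed, examination for adverse effects at those visits, treatment of any infection, a medical monitor (7.8), and capture of concomitant medications (10.1). They limit the harm from an omission and would help to reveal one. They do not replace a prevention measure that the protocol says will be used.

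A reader might also infer uneven infection risk between the two centers, or distorted adverse-event summaries. The documents support neither. They do not say how ablative-arm patients are divided between centers, and section 4.3 recruits everyone from one practice's list. The drugs are oral, so they reach both sides of the face, the adverse-event endpoint compares those two sides within a patient, and section 8.3 makes the safety analysis descriptive.

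**Conclusion.** The point holds as an inconsistency and an operational gap in a patient-safety measure, not as a strict contradiction. Sections 2.3.1 and 6.4 differ on who is covered, what is given and whether it is required, and no procedural section delivers what 2.3.1 promises. Staff working from the procedural sections could omit prophylaxis. A reader might go further and infer that they would, but the documents do not show that, since 2.3.1 remains in force.

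The size is 5 of 15 patients: all 5 for antibiotics, and between 0 and 5 for antivirals, depending on the unstated number with a facial herpes history. The within-patient efficacy comparison is not affected, because oral drugs act on both sides alike. The calculation in section 8.6 uses nothing that depends on prophylaxis.

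The conclusion rests on two assumptions. The first is that the part of the document between the schematic and section 2, which was not available, contains no prophylaxis instruction. The second is that the practice protocols mentioned in 3.1 do not cover anti-infectives. If either is wrong, the remedy reduces to a cross-reference. The change should be made before the first ablative-arm patient is treated.

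**What to change.** Reconcile section 2.3.1 with the prophylaxis section so that both state one policy for each of the three arms: who is covered, which class of drug, and whether it is required or permitted. Carry the agreed policy into the ablative-arm description in the schematic and into the Day 0 procedures in 6.2.2, so that a named step delivers it. If a practice protocol already covers it, cite that protocol in both places. A row in the schedule of events would help but is optional, given how coarse the table is. Check that the consent form describes the same policy.

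Which policy is right is a clinical decision for the investigator, and none is proposed here. The cost is a few sentences and the IRB review that section 9.2 requires for any amendment. Sample size, endpoints and analysis do not change.

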2.3.2 KNOWN POTENTIAL BENEFITS

The laser treatment may improve the subject's aesthetic appearance and therefore the subjects' psychological well-being.

The mask may decrease the patient's skin temperature and therefore pain, erythema and healing time.

3 STUDY DESIGN, OBJECTIVES, AND ENDPOINTS

3.1 DESCRIPTION OF THE STUDY DESIGN

- A Prospective, Multi-Arm, Split-Face, Randomized Clinical Trial
- 2 Study Centers
- Study agent: Velez Intense Hydration Mask
- Study Intervention on Day 0
- Live evaluations by Blinded Evaluators on Day 0
- Daily photographic evaluations by Blinded Evaluators

This will be a prospective, multi-arm, evaluator blind, split-face, clinical trial in which subjects will be randomized to 2 groups in 3 separate arms.

1st Arm (n=5) Non-ablative fractionated Thulium laser (Sciton Moxi)

2nd Arm (n=5) Ablative full Erbium:Yag laser (Sciton Contour)

3rd Arm (n=5) Microneedling with RF (Cutera Secret)

In each arm, there will be two groups

1st group: Velez Intense Hydration Facemask on the left side of their face and nothing on the right

2nd group: Velez Intense Hydration Facemask on the right side of their face and nothing on the left side

Both groups will be utilizing the same safety and comfort protocols established by the practice which include the use of topical numbing cream (B.L.T.) before the laser procedure and cleansing with a makeup wipe and alcohol.

After the procedure a blind evaluator will be grading the subjects' erythema, edema, and any side effects. A compliance analysis performed by study coordinator will be done each visit.

Thirty minutes after the laser procedure, digital photography using Canfield's imaging system, and a thermal camera will be done. In addition, a subject questionnaire on satisfaction, erythema, edema and pain levels after the procedure will be completed. Patients will then have the typical post-care treatment on both sides of their face such as Vaseline for laser resurfacing and a hydrating serum for the Moxi and Microneedling. They will apply the mask at home for at least two hours each day and then return to the office daily for questionnaires and photographs until deemed fully healed by the primary investigator.

3.2 STUDY OBJECTIVES & ENDPOINTS

STUDY OBJECTIVES

3.2.1

Primary: To assess the efficacy of a facial mask in decreasing facial skin temperature after three different aesthetic procedures

Secondary:

[figure not shown]
-To determine the safety and incidence of adverse events when using a Velez face mask after aesthetic procedures

- To assess the change in the level of pain when using a Velez face mask after aesthetic procedures
- To assess patient satisfaction with use of a Velez face mask after an aesthetic procedures
- To assess the reduction of erythema when using a Velez face mask after aesthetic procedures
- To assess healing time when using a Velez face mask after aesthetic procedures

